The goal of the present study is to establish whether delayed discounting is engaged in a WLM intervention that involves EFT, whether this engagement mediates adherence to PA recommendations, and whether environmental factors moderate this relationship. We will do this by testing TST-based mediational pathways in both a standard WLM intervention (Weight Loss Maintenance- Healthy Thinking: WLM-HT) and a

WLM intervention that explicitly seeks to engage DD through EFT (Weight Loss Maintenance+ Future Thinking: WLM+FT). Given that the stated focus of many WLM interventions is on selfregulation^{14,18} and the data linking DD to eating and exercise behaviors^{29,40}, it is reasonable to propose that this putative target is engaged in standard WLM interventions, although this hypothesis has not yet been empirically tested. At the same time, we recognize that there is tremendous variability in response to WLM interventions⁶, which suggests the need to more systematically engage putative targets such as DD to improve behavioral adherence and long-term outcomes. EFT is a promising strategy but has yet to be explored in WLM. Thus, testing of the DD mediational pathway within these two interventions will allow for both within- group examinations of the hypothesized mechanism of action as well as between-group comparisons of whether explicit engagement of DD results in greater behavioral adherence and improved WLM outcomes. It is hypothesized that 1) Compared to WLM-HT, WLM+FT will produce more engagement of DD and PA adherence as measured by EMA and accelerometry. 2) In both WLM-HT and WLM+FT, within-person mediational pathways will be found between participation in the intervention and PA and changes in delayed discounting on 2a) a daily basis (EMA) and 2b) over longer-time periods (1- and 3-month change predicting PA outcomes at 6 months). 3) Environmental context will moderate the mediational pathways in both interventions such that DD will be a stronger determinant of behavior in environments with more proximal costs than in environments with more proximal benefits.

Design, Procedures, Materials, and Methods.

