Overview. Consistent with contemporary WLM trial designs^{41,[57]} this study involves two phases: a weight loss induction phase and a maintenance phase. While early maintenance trials recruited individuals from the community who had already lost weight⁴², more recent studies (e.g., Weight Loss Maintenance Trial⁴¹) have included a weight loss induction phase. This approach facilitates recruitment and ensures that the sample is at similar stages of the weight management cycle, thereby optimizing methodological rigor^{41,43-46}. During **Phase I**, 160 individuals will enroll in our existing 16-week Internet weight loss program. Those who achieve a $\geq 5\%$ ⁴⁷ weight loss will be invited to participate in Phase II, the actual maintenance trial. Given our previous experience with the weight loss intervention^{44,48,49}, we anticipate that 54% of participants who enter Phase I will reach the $\geq 5\%$ goal and be eligible for Phase II. While we have substantial data to support this estimate from 4 large trials, if necessary, given the low cost of this intervention, we can adjust the Phase I N to ensure that we reach the Phase II target N for which the trial is powered. In **Phase II**, participants (N=70) will be randomized to (1) Healthy ThinkingWLM (WLM-HT)^{42,50} or (2) WLM with Episodic Future Thinking cues⁵¹ to reduce delayed discounting (WLM+FT). Both interventions will be 4- months long and involve 7 in-person group sessions. Our team is known for high retention rates (90-98%)^{44,49,52} and we have demonstrated our ability to meet our Phase I recruitment goal (N=160). In recent trials,^{44,52,53} we enrolled an average of 200 participants/year. UConn's Institute for Collaboration on Health, Intervention, and Policy, an exceptional environment in terms of physical resources and research collaboration. Thus, we are confident we have the resources and experience to meet recruitment goals. Participants will be recruited in 2 cohorts. For each cohort, we will recruit N=70 into Phase 1, with the expectation that at least N=35 from each cohort will be randomized in phase II.

PHASE I APPROACH

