Treatment Components Specific to the WLM-HT intervention. Similar to participants in WLM+FT, participants in WLM-HT will be accessing daily cues on our study website. The difference will be that, rather than EFT cues, these cues will focus on healthy living tips (e.g., Greek yogurt is a great source of protein and calcium). To increase adherence, participants will receive two reminders per day via text and/or email to log onto the website to read their physical activity cues. These reminders may include image messages. After the cue, they will be asked brief questions to enhance the affect of the cue (e.g., How are you keeping in mind your cue during the day). Participants will choose their healthy living tips from a list provided to them with their case manager at their in-person sessions (2, 30-60 minutes at the start and mid-way through treatment), or over the phone if the participant wishes to change their tips at other times during Phase II treatment. Case-managers will speak on the phone with participants weekly (for approximately 10 minutes) to briefly check-in about cue-use and to change/replace any cues if the participant wishes to.

Phase II Assessments. Assessments will occur at baseline (start of Phase II) and 1, 2, and 4 months later. EMA allows for a fine-grained analysis of how putative factors operate in the real-world environment in which behavioral decisions are made. The intensive within-participant assessment of DD and environmental factors will provide a rich test of how EFT engages DD and how engagement of DD impacts PA over the course of the day or week, precisely the type of data that is needed to inform our theories and interventions. All study visits will be conducted at our office on the 6th floor of [name].

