Attentional Bias: measured by Dot Probe tasks will be used to assess attentional bias towards food⁸⁰. On these tasks, participants are asked to watch the screen while 2 images are briefly presented. A dot then appears and participants are asked to identify which side of the screen it was presented (i.e. left vs right) as quickly and accurately as they can. Both food and non-food pictures will be used and both discrimination and reaction time will be assessed. _____

Given that depression can negatively affect cognitive functioning⁹⁷, the Center for Epidemiologic Studies Depression Scale (CES-D)⁹⁸ will be used to account for contribution of mood symptoms to cognitive functioning scores. Given that this is a screening tool, participants will be given referrals for mental health treatment if they score in the clinical range (16 or above).

To clarify the independent contribution of DD and executive functioning on PA, the **Spot-the-Word test** will be used to estimate full-scale intelligence. It will be utilized as a covariate in analyses to clarify the relative contribution of global vs. specific cognitive abilities on outcomes. Spot-the-Word is a well validated test based on lexical decision making which is highly correlated with verbal intelligence. This test was normalized on a sample stratified by age and socio-economic status and is relatively resistant to the effects of age, brain damage, and stress (N=224).⁶⁴

Delayed Discounting. We will administer a clinic-based, adaptive computerized assessment of delayed discounting^{60,61}, at the start of weight loss maintenance and 1, 2, and 4 months later. This task asks participants to choose between less value now and greater value in the future (e.g. “would you rather have \$50 now or \$100 in two weeks”). A brief version of this task will be used for EMA assessment to capture the immediate effects of EFT on DD. The steepness of the DD curve will be examined across indifference points (i.e. when one opts for less sooner vs. now later across different time delays) to calculate a k discounting function.

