Physical Activity (Primary Outcome). The validated^{83,84} Actigraph GT9X will be worn on the waist for 7-days at Phase II 0,1, 2, and 4 months. Data will be processed with the ActiLife software, ensuring wear time requirements and validated algorithms. Time spent in MVPA and bout-related MVPA (≥ 10 min in duration) will be examined. In addition, following [name] et al.’s protocol that has been validated against accelerometry^{75,77}, each EMA prompt will include questions about activity type and purpose that cannot be captured by accelerometers. To allow for future direct comparisons of Phase I processes, we will also administer the Paffenbarger (PAQ)^{62,63}.

Weight (Secondary Outcome). Weight will be measured to the nearest 0.1kg with a digital scale. Participants will be measured wearing one layer of clothing without shoes. Weight will also be measured objectively at each WLM session and reported over the phone to case-managers on a weekly basis.

Environmental Context (Moderators). EMA measures of the environment focus on factors that may alter the cost/benefits of PA. On each EMA prompt, participants will be asked to indicate their current physical and social context. Following Elliston et al.²⁴, participants will be asked whether they can see others in their environment being physically active (**norms**), whether a TV or computer can be seen from where they are sitting/standing (**sedentary options**), and whether exercise equipment is available or if they are within a 5- minute walk to a place they can be physically active (**accessibility**). We will then ask, consistent with Booker & Mullan⁸⁵, about 5 potential PA triggers (physical, sensory, social, internal, and external drives; e.g., “Right now, are there any social triggers in the environment which are influencing your physical activity”). The mean of the 5 items will be used to create an **environmental responsiveness** score. Consistent with other EMA protocols⁸⁶, **stress** will be assessed with 3-items of the Perceived Stress Scale⁸⁷ adapted for momentary use (e.g., “How stressed do you feel right now”) and **social support** will be measured with 1-item⁸⁸. Local **weather** indices will be obtained for the EMA dates from a national weather service, as we have done in a prior study⁸⁹.

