Additional Temporal Self-Regulation Theory Measures. To test the full TST model, we will supplement EMA with clinic-based assessments of intentions⁷², habits⁹⁰, and temporal contingency^{15,91}. The following validated environment measures will also be administered: Weight Related Social Norms⁹² adapted for PA, Exercise Environment Questionnaire¹³ and a survey on sedentary activity options¹⁴ (accessibility; sedentary options), Environmental responsiveness²³, Perceived Stress Scale⁸⁷, and the Social Support and Exercise Survey⁹³, Physical Activity Enjoyment Scale⁹⁹, Behavioral Regulation of Exercise Questionnaire¹⁰⁰, Self-efficacy for exercise¹⁰¹, CHAOS¹⁰¹, and the Three Factor Eating Questionnaire- 18¹⁰². These measures are reliable and sensitive to obesity or eating behaviors, and for EF.

Additionally, frequency of self-weighing will be assessed in phase II assessments as it has been found to be a predictor of weight maintenance¹⁰⁴.

Treatment acceptability will be measured using a questionnaire adapted from prior weight control and EFT studies⁵¹.

Phase II Summary of Time Commitment

9 in-person treatment sessions (7 groups, 2 case-management) over the course of 4 months, each 30-90 minutes in duration

Approximately 14 phone calls (about 15 minutes each) with a case manager, on weeks when there is not an in-person case management session.

4 assessments are completed in our office at 0 (90 min), 1 (30 min), 2 (60 min) and 4 months (60 min).

Accelerometry data is collected for 7 days at 0, 1, 2, and 4 months.

EMA will be conducted for 7 days at 0, 2, and 4 months.

Phase I & II contingency plan for assessment procedures during national emergencies such as COVID-19.

Because assessments take place in person, alternative remote procedures will be implemented in the case that in-person contact poses a health risk to participants. In these cases, data will be collected using the following methods:

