Primary hypothesis 2: Within-person mediational pathways will be found between participation in the intervention and PA and changes in DD on 2a) a daily basis (EMA) and 2b) over longer-time periods (1- and 2month change predicting PA outcomes at 4 months). Using mixed-effects mediation modeling assuming time points clustered within individuals with Mplus and mediation package from R[104-107], we will test how the relationship between intervention condition and PA is mediated by change in DD over time by using daily data and also running prediction models by the four time points. DD will be evaluated for normality and linearity assumptions and if assumptions are violated, GLM models will be established to determine the indirect effect.

Exploratory hypothesis: Environmental context will moderate the mediational pathways such that DD will be a stronger determinant of behavior in environments with more proximal costs. A moderated mediation mixedeffects model will test the strength or weakness of the indirect effect and/or the direct effect of the intervention condition on PA by the different environmental factors measured. The mixed-effects will consider effects by the daily data collected within the four general time points nested within individuals.

Missing data. We will run a systematic analysis of missing EMA data to determine whether the likelihood of response at any given prompt is time-varying (e.g., time of day/week, activity level). We anticipate approximately ~80% of prompts will be answered⁷⁵. If needed, we will use multilevel data imputation strategies ⁹⁴. For clinicbased data, type of missingness will be evaluated and values will be imputed using full information or restricted maximum likelihood estimation ⁹⁵. All variables in our models will be used to impute missing data. Sensitivity analyses will be used to compare results with and without imputed values.

Inclusion/Exclusion Criteria.

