Participants in this study will be 160 healthy overweight or obese men and women ages 18-70 recruited from the greater Hartford, Connecticut area. Participants will have a body mass index between 30 and 50 kg/m². This weight criterion was chosen because of the high prevalence of overweight and obesity in the United States and because of the health implications associated with obesity. We have chosen a BMI upper limit of 50 kg/m², as individuals with a BMI greater than 50 have more medical co-morbidities and require greater medical supervision and eligibility screening. Additionally, as the EMA protocol will require answering questions on a smartphone app several times a day, participants must have a smartphone and use text and/or email on a daily basis to be eligible.

Participants will be excluded if they report being unwilling to complete accelerometry or EMA protocols, are unable to walk 2 blocks without stopping; are currently participating in a weight loss program, taking a weight loss medication, have a history of bariatric surgery, or lost ≥ 5% of body weight during the past 6-months; are pregnant, lactating, less than 6 months post-partum, or plan to become pregnant during the time frame of the investigation; report a medical condition that would affect the safety and/or efficacy of a weight management program involving diet and physical activity (e.g., uncontrolled heart problem); have a history of Multiple Sclerosis, traumatic brain injury or other neurological disorders; or report conditions that in the judgment of the Principal Investigator (PI) would render them potentially unlikely to be able to follow the protocol for 9 months, including terminal illness, plans to relocate, substance abuse, dementia, bulimia nervosa, or other significant psychiatric problems. Participants taking prescription medications, reporting joint problems, heart disease, or other medical conditions that are affected by weight loss or may limit their ability to exercise will be required to obtain written approval to participate in a weight loss program from their physician. During times of national emergency (e.g., COVID-19), participants unable or unwilling to engage in videoconference meetings will be excluded. Participants may be removed from the study by the PI if they are consistently (i.e. across several group

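### Hypothesis 2b is stated with two different horizons, and its month-4 activity model names no adjustment for baseline activity

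*Combined protocol and SAP*

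**What the plan says.** The last paragraph of the Purpose / Introduction section lists the hypotheses. Its item 2b looks at mediation "over longer-time periods (1- and 3-month change predicting PA outcomes at 6 months". The Analyses section restates the hypothesis under the label Primary hypothesis 2, this time "over longer-time periods (1- and 2month change predicting PA outcomes at 4 months".

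The design sections agree with one another on timing:

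- Overview, on Phase II: "Both interventions will be 4- months long and involve 7 in-person group sessions".
- Phase II Assessments: "Assessments will occur at baseline (start of Phase II) and 1, 2, and 4 months later".
- Delayed Discounting (clinic task): "at the start of weight loss maintenance and 1, 2, and 4 months later".
- Physical Activity (Primary Outcome), on the accelerometer: it "will be worn on the waist for 7-days at Phase II 0,1, 2, and 4 months".
- Phase II Summary of Time Commitment: "EMA will be conducted for 7 days at 0, 2, and 4 months".

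For hypothesis 2 the plan is mixed-effects mediation with change in DD as the mediator between arm and PA. It is to be run on the daily data and as prediction models over the four time points. The text on hypothesis 2 names no covariates. Those named elsewhere are demographics that differ between arms at baseline, an intelligence estimate, and a depression score to account for mood in the cognitive scores. Month-0 PA is not among them.

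**The concern.** In a lagged mediation hypothesis, the mediator interval and the outcome time are part of the definition. Two versions in one current document leave open which was prespecified. Someone comparing the final report with the Introduction could conclude that a hypothesis was altered or that a 6-month outcome was dropped.

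The second issue is the path from DD change to later PA. Randomisation supports the comparison of arms on DD and on PA. It does not support the DD-to-PA path, because participants are not allocated to a change in DD. The Introduction also wants the pathway examined within each arm, where there is no randomised contrast at all. If people who begin maintenance more active also tend to show a larger shift in DD, and activity persists, DD change will predict month-4 PA without causing any of it.

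**Working it through.** **1. Time points side by side.**

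| Source | Mediator change at | PA outcome at |
|---|---|---|
| Introduction, 2b | months 1 and 3 | month 6 |
| Analyses, Primary hypothesis 2 | months 1 and 2 | month 4 |
| Clinic DD schedule | 0, 1, 2, 4 | – |
| Accelerometer schedule | – | 0, 1, 2, 4 |

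Of the Introduction's times {1, 3, 6}, only month 1 is in {0, 1, 2, 4}. All of the Analyses section's times {1, 2, 4} are.

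**2. Is the 4-month length itself secure?** Yes. The taper in Treatment Components Common to Both Conditions gives 2 weekly + 3 fortnightly (over six weeks) + 2 monthly = 7 sessions, as stated. The time-commitment summary gives about 14 calls, and 16 weeks − 2 case-management weeks = 14.

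**3. Could the Introduction be counting from the start of Phase I?** Phase I lasts 16 weeks: 16 × 7 / 30.4375 = 3.68 months. On that clock the Phase II visits fall at about 3.7, 4.7, 5.7 and 7.7 months. Two of these lie near 3 and 6, but the reading fails. Phase I is assessed only before and after treatment, so no month-1 change exists. A DD change completed during Phase I would also precede randomisation and could not carry an effect of the arm.

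**4. Does any planned figure depend on this?** No. The Power section uses four time points per participant with an intraclass correlation of 0.25. Months 0, 1, 2, 4 make four time points, and so do 0, 1, 3, 6. The stated 82.1% is the same under either.

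**5. Baseline PA in the month-4 model.** Let X be month-0 PA, D the DD change to month 1 or 2, and Y month-4 PA, all standardised. Suppose

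Y = b·X + c·D + error, with correlation a between D and X.

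Regressing Y on D alone gives a slope of c + a·b. Including X gives c. The bias is a·b, and it is zero only if a or b is zero.

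- b: activity is likely to persist, and people are expected to enter Phase II already active, because Phase I works up to 250 minutes a week. The Introduction reports 245.8 ± 174.6 PA minutes at 6 months in the team's own earlier work, a coefficient of variation of 174.6 / 245.8 = 0.71. That is not a Phase II baseline figure, but it shows how widely people in such a programme differ.
- a: the documents give no estimate.

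The bias therefore cannot be sized from the documents. Its mechanism is clear and the covariate that addresses it is on file.

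**6. Why not adjust for PA at the month-1 or month-2 visit as the main analysis?** Let D raise same-visit PA by d, and let that PA carry over to month 4 with coefficient m. The full effect of D is then its direct part c plus d·m. Conditioning on same-visit PA leaves only c and removes d·m, which may be part of what 2b is looking for. Month-0 PA precedes any DD change and does not raise this problem.

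**The case against.** The strongest reply on timing is that the Introduction contains one uncorrected parenthesis. The Introduction does not label its hypotheses primary; the Analyses section does, and its version fits every design section. This stands. A reader might infer from the Introduction that hypothesis 2b cannot be tested, or that a 6-month follow-up has been left out. The documents support neither reading: the operative analysis uses only visits that exist, and no section schedules anything after month 4.

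A reader might also set the 4-month end against the document's language on sustained or long-term results and infer an unmet promise of durability. That language sits mainly in background and in the statement of significance. The stated goal is whether DD is engaged, whether it mediates adherence, and whether environment moderates the pathway.

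On baseline PA, the reply is that a mixed model over four time points plausibly already contains month-0 PA as one of the repeated outcomes, and that the section is merely brief. This stands in part: the plan does not commit to an unadjusted association. But it names neither the covariates nor the handling of earlier PA, and having month-0 PA among the responses does not by itself condition the DD-to-month-4 path on it. A reader might go further and infer that 2b would produce false-positive findings at some specific rate. That would need correlations the documents do not report.

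**Conclusion.** The point holds as an inconsistency plus an unspecified covariate. Two of the three time points for hypothesis 2b in the Introduction do not exist in Phase II; the Analyses section's version is measurable throughout. Correcting the Introduction alone is close to an editorial matter, though worth doing because it fixes the definition of a hypothesis that the Analyses section calls primary.

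The more substantive part is that the non-randomised path from DD change to month-4 PA names no baseline PA adjustment. The direction and size of any bias depend on how month-0 PA relates to DD change and to month-4 PA, and the documents do not quantify either. The algebra assumes linear relations and no other confounder, so the adjustment removes one plausible source of bias and does not make the path causal. Design, sample size and stated power are unaffected.

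**What to change.** 1. In the Purpose / Introduction section, reword hypothesis 2b to 1- and 2-month change predicting PA at 4 months, in agreement with the Analyses section and the visit schedule.
2. In the Analyses section, under Primary hypothesis 2, state that the month-4 PA model for 2b includes month-0 accelerometer PA as a covariate, in the same metric as the outcome.
3. If adjustment for PA at month 1 or 2 is wanted, list it as a sensitivity analysis and say that it may remove part of a true effect.

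The cost is one line in the Introduction and one named covariate. No new data are needed: month-0 accelerometry is already scheduled, and the Randomization section requires Phase II baseline measures to be complete before allocation, so the covariate should be largely complete. The adjusted estimate may differ from the unadjusted one, so the change should be recorded before outcome data are analysed.

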Phase I Assessments. Given that the primary purpose of Phase I is to efficiently induce weight loss for Phase II, assessments will be minimal. Pre- and post-treatment assessments will be relatively minimal, taking approximately 45-minutes to complete. The following will be collected:

Demographics. Demographics (e.g., sex [male, female, non-binary], age, income) will be collected at pretreatment only.

Weight and height. At both pre- and post-treatment, weight will be measured to the nearest 0.1kg using a digital scale. Height will be measured to the nearest millimeter using a stadiometer (baseline only). Participants will be measured wearing light, indoor clothing without shoes.

Maintenance treatment mechanisms. While Phase I processes of change are not the focus of the study, we will include pre-post tests of delayed discounting^{60,61} (see phase II measures) and PA. Accelerometry will be used in Phase II (focus of study) but not in Phase I for cost and efficiency reasons. Instead, the **Paffenbarger Activity Questionnaire (PAQ)**^{62,63}, will assess the hours/day an individual spends doing various levels of physical activity in a typical weekday and weekend day. The PAQ is frequently used in the field and has been found to have good validity and reliability among adults.

Financial literacy will also be assessed at baseline to clarify any role that financial literacy may play in Delay Discounting scores⁹⁶.

We will also ask participants to tell us their mobile phone service provider. Our Phase II treatment website will need to be adapted slightly for rare service providers that we have not yet come across, so we need to determine if we need to make these adaptions during Phase I of the program.

PHASE II APPROACH

Participants. Those who lose at least 5% of initial body weight during Phase I (N=70) will be eligible to participate in Phase II, the weight loss maintenance trial (i.e. the primary focus of the application). Given our previous findings^{44,52,53,59}, we anticipate that the demographic characteristics of participants entering Phase II will be similar to those of participants in Phase I. In addition, in a previous trial in which we used the proposed two phase maintenance design with Phase I as the Web program, we found that 99% of participants who met the 5% weight loss criterion in Phase I elected to continue into Phase II⁴⁴.

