Power. Based on prior DD and EFT work^{31,34,39}, power is computed for an effect size (d) of 0.50. The computations assume an intraclass correlation (ICC) of 0.250 for the 4 time points clustered within each participant. The standard deviation is assumed to be the same in the two conditions. The criterion for significance (alpha) has been set at 0.05. The test is 2-tailed, which means that an effect in either direction will be interpreted. Given these assumptions, the study will have 82.1% power to yield a statistically significant result that will increase in one unit per number of individual covariate(s) included in the models. Accounting for 15% attrition, 15 more participants will be added, so a total of 160 participants will be enrolled in Phase I.

Analyses.

Primary hypothesis 1: WLM+FT will produce more engagement of DD and PA adherence. Descriptive statistics will be generated on all the demographic variables as well as mediators (DD), moderators

(environmental variables), covariates (WAIS-II) and outcomes (PA and weight). Differences between WLM-HT and WLM+FT will be assessed through chi-square tests (proportions) or Student's t-test (means) at each time point; if differences on any of the demographics are found at baseline, the variable will be used as a covariate in the main model. The main outcome, PA distribution data will be examined and if variables violate distributional assumptions of normality, will be analyzed using generalized linear model (GLM) procedures, which enable the use of non-Gaussian error models. Using a mixed-effects model in Mplus we will be able to estimate the main effect of the intervention considering the four time points nested within individuals allowing for time-varying effects of covariates to vary with time for the daily data collected.

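### Hypothesis 2 names no baseline confounders and no sensitivity analysis for the non-randomised path from delay discounting (DD) to physical activity (PA), which leaves 2b and any uncentred model open to confounding

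*Combined protocol and SAP*

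**What the plan says.** The introduction gives the goal as establishing whether DD is engaged and "whether this engagement mediates adherence to PA recommendations". Under *Analyses, Primary hypothesis 2*, "we will test how the relationship between intervention condition and PA is mediated by change in DD over time", using the daily data (2a) and the assessment time points, with early DD change predicting 4-month PA (2b). The pathways are described as within-person. That paragraph lists no covariates, no assumption about unmeasured confounding and no sensitivity analysis for the indirect effect. The only sensitivity analysis, under *Missing data*, compares results with and without imputation.

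On covariates the plan says four things elsewhere:

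- *Phase I Assessments*: age, sex and income are collected before treatment, and "Financial literacy will also be assessed at baseline to clarify any role that financial literacy may play in Delay Discounting scores". The analysis section does not mention financial literacy again.
- *Analyses, Primary hypothesis 1*: "if differences on any of the demographics are found at baseline, the variable will be used as a covariate in the main model".
- *Phase II Assessments*: Spot-the-Word is a covariate, whatever the arm balance, to isolate what DD and executive function contribute to PA. CES-D is to account for mood in the cognitive scores. The analysis section names WAIS-II as the covariate, a test described nowhere else.
- *Randomization*: age is a stratification factor. It is not named as a model term.

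**The concern.** Randomisation protects the effect of arm on DD and of arm on PA. It does not protect the association between DD and PA given arm. A person's age, income, financial literacy, general ability or mood could influence both. If so, DD and PA are associated within each arm even when DD does nothing, and the indirect effect picks that up.

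A test for baseline arm differences does not help. Under randomisation it flags any given variable about 5% of the time, however strongly that variable drives DD and PA. A variable can be perfectly balanced between arms and still be a common cause within both. The plan itself treats financial literacy as a possible influence on DD scores, measures it, and then gives it no analysis.

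At stake is the conclusion the trial was built for: whether an observed DD–PA association may be read as mechanism.

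**Working it through.** **1. The plan's own figure, and the sample size it implies.** Inputs from *Power*: "power is computed for an effect size (d) of 0.50", together with an ICC of 0.25 over four repeats per person and a two-sided 5% test. The variance factor for a mean of four repeats is (1 + 3 × 0.25)/4 = 0.4375. The noncentral t with 30 per arm gives 82.09%, matching the stated 82.1%. With 35 per arm it gives 87.6%, which does not match. The stated power therefore refers to about 60 completers (70 × 0.85 = 59.5). The 60 is inferred; the plan does not print it. Equal allocation is assumed. This power covers the arm comparison only, not the DD-to-PA path.

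**2. A factor related to DD change (2b).** Assumptions: 30 per arm; arm effect on DD change 0.5 SD; true DD-to-PA effect zero; one baseline factor correlated r with both DD change and PA. PA is regressed on arm and DD change.

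- Spurious slope = r × r / 1 = r².
- Standard error ≈ √[(1 − r⁴)/57], with 57 = 60 − 3.
- False-positive rate ≈ P(|Z + r²/SE| > 1.96).

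| r | slope | slope/SE | rate, formula | rate, simulation | rate under arm-imbalance rule, simulation |
|---|---|---|---|---|---|
| 0.2 | 0.04 | 0.30 | 6% | 6–7% | 6–7% |
| 0.3 | 0.09 | 0.68 | 10% | 10% | 10% |
| 0.4 | 0.16 | 1.22 | 23% | 23% | 22% |

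Entering the factor in the model returns the rate to about 5% throughout.

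**3. The mediation conclusion rather than the single path.** The plan names no test for the indirect effect. If both paths must be significant, the arm-to-DD test matters. With 0.5 SD and 30 per arm, 0.5/√(2/30) = 1.94, so its power is about 0.49. The products are 0.49 × 6% ≈ 3%, 0.49 × 10% ≈ 5% and 0.49 × 23% ≈ 11%; simulation gives about 3%, 5% and 10%. Without confounding the same requirement would give 0.49 × 5% ≈ 2.5%.

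**4. A factor related only to DD level.** If the factor shifts DD equally at both visits, it cancels from the change score. The simulated slope is 0.00 and the rejection rate about 5% at every r tried. If baseline DD is also put in the model, the cancellation is lost: the rates become about 5%, 7% and 11% at r = 0.2, 0.3 and 0.4. These depend on the assumed visit-to-visit correlation of DD, which the plan does not give.

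**5. Within-person and between-person slopes.** Four repeats, ICC 0.25 assumed for both DD and PA, true effect zero, a fixed trait with r = 0.2, 0.3, 0.4:

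| slope | bias |
|---|---|
| person-mean-centred | 0.00, 0.00, 0.00 |
| random intercept, DD uncentred | 0.02, 0.05, 0.09 |
| between-person | 0.09, 0.20, 0.37 |

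The last row agrees with r²/0.4375 = 0.09, 0.21, 0.37. The plan does not say which slope it will estimate.

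**The case against.** The strongest reply is that hypothesis 2 is described as within-person, and fixed traits cannot bias a within-person slope. That stands for 2a if DD is centred on each person's mean. It does not cover 2b, where early DD change predicts later PA across people, or an uncentred model. No centring is specified, and the exposure, arm, is itself fixed for each person.

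Second, financial literacy is collected for its bearing on DD scores, which are levels, while the mediator is change in DD. This also stands: step 4 shows no bias from a level-only factor in an unadjusted change score. The protection goes if the factor also predicts change, or if baseline DD enters the model.

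Third, the plan does adjust for something. Spot-the-Word is committed for exactly this question, and CES-D is tied to the cognitive scores, among which DD is listed. A reader might infer that the path has no adjustment at all; the documents do not support that. Nor do they apply the arm-imbalance rule to hypothesis 2: it appears under hypothesis 1 for the main model, and the hypothesis 2 text is silent.

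Fourth, the documents show no relation of age, income or financial literacy to PA. They give no value of r, so a material bias is possible but not demonstrated.

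**Conclusion.** The point holds as a gap in specification. The DD-to-PA path has no stated set of baseline confounders beyond one ability measure, and no analysis of what unmeasured confounding would do to the indirect effect. The only demographic rule in the plan is not a confounding criterion. The exposure is chiefly in 2b and in any uncentred model.

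The size is conditional. If a baseline factor correlates with both DD change and PA, the path is falsely significant about 6–7%, 10% and 23% of the time at r = 0.2, 0.3 and 0.4. If mediation also requires a significant arm-to-DD path, this becomes about 3%, 5% and 10%, against about 2.5% with no confounding. The effect is small at 0.2 and material for the path from about 0.3. These figures assume about 60 completers and a 0.5 SD arm effect on DD change.

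A reader might go further and infer that hypothesis 2 as a whole is confounded, or that false mediation claims will occur at the single-path rates. The documents support neither. A person-mean-centred 2a slope is not biased by fixed traits, a level-only factor leaves an unadjusted change score unbiased, and the single-path rates are not the rates of a mediation conclusion. The stated power for the arm comparison is unaffected.

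**What to change.** In the hypothesis 2 models:

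1. Enter age, income, financial literacy, Spot-the-Word and baseline CES-D in both the DD equation and the PA equation, whatever the arm balance. Use values taken before Phase II randomisation. Reconcile WAIS-II with Spot-the-Word in the analysis section.
2. In the daily models, split DD into the person mean and the deviation from it, and say which term tests hypothesis 2a.
3. For 2b, state whether the change score is adjusted for baseline DD, since that decides whether factors affecting only DD level matter.
4. For 2b, report how large a correlation between the errors of the DD and PA equations would bring the indirect effect to zero. Word the mediation conclusion as conditional on no unmeasured confounding.

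The variables are already in the assessment schedule, so the change is text and a little code. It costs about five degrees of freedom at roughly 60 completers, more if income is entered in categories. As a guide, five covariates move the arm-comparison power from 82.09% to 81.97%, counting lost degrees of freedom only. The other cost is a mediation claim that carries a stated caveat.
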